5.2.1 Risk-Benefit Considerations

Despite substantial technical improvements in imaging modalities that have an impact on image quality on the equipment side, approximately 30% of patients continue to undergo stress echocardiographic examinations that are non-diagnostic or inconclusive due to poor image quality, with subsequent poor evaluation of cardiac function, leading to the need for more invasive techniques.^{1,12,30} These patients would benefit from a contrast agent that can opacify the LV and improve the delineation of EBs.

Given the fact that the subjects to be enrolled in the present clinical trial will be subjects already having suboptimal echocardiographic images and have no evidence of intracardiac shunts, inclusion in the study is unlikely to add any risk for the subjects. Due to the fact that subjects who are contraindicated for dobutamine will already be excluded from this study, dobutamine used as the stressor in this study will not add any additional risk to the subjects.

Even though the subjects have been scheduled for coronary angiography most likely have already undergone other diagnostic imaging modalities such as DSE or SPECT, the contrast enhanced DSE will still add incremental value with better EBD which will translate into better recognition of wall motion abnormalities. Furthermore, CEUS stress echocardiography will prevent the risk of those subjects being exposed to radiation through other imaging modalities in the down streaming of appropriate assessment of cardiac function and structures.

LUMASON efficacy and safety is based on data from 75 clinical trials in 6307 subjects and post-marketing surveillance over 12 years of market use in an estimated 2.7 million patients.

Hypersensitivity to any of the components of LUMASON, as for other contrast agents, cannot be excluded, and there is potential for unpredictable, serious hypersensitivity reactions, including anaphylactoid reactions. Further, such reactions may lead to life-threatening conditions if they occur in critically ill patients. However, serious hypersensitivity reactions after LUMASON administration are rare (estimated occurrence of approx. 1 in 10,000 exposures) and suboptimal EBD and inaccurate assessment of LV function (global and regional wall motion assessment) and/or cardiac anatomy are frequent in a patient population with suspected CAD.^{12,13,31}

Echocardiography is an imaging modality that represents a fundamental investigation used in the initial and ongoing management of patients with suspected or known CAD because it is noninvasive, provides easy access, anytime and any day, can be performed at the bedside of the patient, and can be repeated as often as needed for monitoring. The balance of the benefit of LUMASON in comparison with its risks is also positively affected by the availability of acute

care settings and physicians that can promptly and effectively recognize and manage serious adverse events.

Although optional noninvasive modalities (SPECT, CMRI and CT angiography) may provide diagnostic accuracy, valuable and detailed data, all of them pose greater risk than transthoracic echocardiograms.^{32 33} Probably the most critical drawback is the time delay in obtaining the data needed for urgent risk assessment and treatment, but safety concerns including exposure to radioactive material and risky patient transportation to the nuclear/MRI department are also present.²¹ Furthermore, if an imaging agent is used, these imaging modalities carry the same risk of rare, serious hypersensitivity reactions and the same risk of serious, life-threatening complications.

Of note, at the patient level, the effective dose of a single nuclear cardiology stress imaging scan ranges from 10 to 27 mSv. The corresponding equivalent dose exposure is 500 chest X-rays [Cardiolite® (Tc-99m Sestamibi)], 1200 chest X-rays (Thallium) and 1300 chest X-rays (with dual imaging protocol). According to the latest estimates the risk of cancer for a middle aged patient ranges from 1 in 1000 (for Cardiolite) to 1 in 400 (for a dual isotope scan).²¹ Therefore, contrast-enhanced stress echocardiography should be preferred due to wider availability and for its radiation free nature. Overall, the effectiveness and suitability of LUMASON as a contrast agent for use with echocardiography to obtain improve LV EBD has been demonstrated. Clinical studies have shown LUMASON to be safe and well tolerated with minimal risk to subjects. In conclusion, the benefit-to-risk ratio for LUMASON is high, indicating an advantage to subjects undergoing stress echocardiography.

With the marked increase in costs associated with cardiovascular care and interventions, it is vital that non-invasive imaging procedures be highly accurate in detecting whether a patient is at risk for coronary events, not just whether they have a significant coronary stenosis. It is also vital that these stress imaging procedures be equally accurate in identifying which patients are at risk for future cardiac events.

5.3 Study Duration

The procedure associated with the LUMASON administration will be completed within approximately 1 hour. Safety monitoring will begin at the time of signing Informed Consent and continue for 72 hours after the last LUMASON administration or until the subject undergoes cardiac intervention, whichever comes first. Subjects will be followed up to 6 months to collect truth standard data (coronary angiography or cardiac events) as described in Section 8.6.4.

5.4 Study Population

The study will be conducted in subjects who have suboptimal image quality on UEUS echocardiography at rest and are scheduled for coronary angiography. It is expected that 10-15 study centers will participate in the study. Approximately 175 subjects will be enrolled in order to obtain 45 subjects with positive CAD and 45 with negative CAD based on the truth standard. The prevalence of positive CAD subjects will be tracked based on the onsite diagnosis of CAD from the truth standard. If the overall yield of positive CAD subjects is lower than the assumed

30%,³⁴ then additional subjects will need to be enrolled in order to obtain a sufficient number of positive CAD subjects.

5.4.1 Inclusion Criteria

Enroll a subject in this study if the subject meets the following inclusion criteria:

- Provides written Informed Consent and is willing to comply with protocol requirements;
- Is at least 18 years of age;
- Has suspected or known CAD and is scheduled to undergo coronary angiography within 6 months after the LUMASON DSE.
- Has undergone a previous echocardiography prior to enrollment; resulting in suboptimal unenhanced images at rest, defined as ≥ 2 suboptimal adjacent segments in any apical view.

5.4.2 Exclusion Criteria

Exclude a subject from this study if the subject does not fulfill the inclusion criteria, or if any of the following conditions are observed:

- Is a pregnant or lactating female. Exclude the possibility of pregnancy:
 - by testing on site at the institution (serum or urine β HCG) within 24 hours prior to the start of LUMASON administration(s),
 - by surgical history (e.g., tubal ligation or hysterectomy),
 - post menopausal with a minimum 1 year without menses;
- Has any known hypersensitivity to 1 or more ingredients of LUMASON (sulfur hexafluoride or to any components of LUMASON);
- Has any known hypersensitivity to dobutamine;
- Has an ongoing or recent (within the last 30 days) acute myocardial infarction;
- Has known right-to-left, bidirectional or transient cardiac shunt (ruled out with agitated saline study performed before administration of LUMASON);
- Has electrolyte (especially potassium and magnesium) abnormalities;
- Has unstable pulmonary and/or systemic hemodynamic conditions e.g.:
 - decompensated or inadequately controlled congestive heart failure (NYHA Class IV);
 - hypovolemia;
 - uncontrolled hypertension, i.e. resting systolic blood pressure >200 mmHg or diastolic blood pressure >110 mmHg;
 - unstable angina;
 - acute coronary syndrome;
 - aortic dissection;
 - acute pericarditis,
 - myocarditis, or endocarditis;
 - stenosis of the main left coronary artery;

- hemodynamically significant outflow obstruction of the left ventricle, including hypertrophic obstructive cardiomyopathy;
- hemodynamically significant cardiac valvular defect;
- acute pulmonary embolism;
- Has uncontrolled cardiac arrhythmias;
- Has significant disturbance in conduction;
- Has hypertrophic subaortic stenosis;
- Has an acute illness (e.g., infections, hyperthyroidism, or severe anemia);
- Was previously entered into this study or received an investigational compound within 30 days before admission into this study;
- Has been treated with any other contrast agent either intravascularly or orally within 48 hours of the first LUMASON administration;
- Has any medical condition or other circumstances which would significantly decrease the chances of obtaining reliable data, achieving study objectives, or completing the study and/or postdose follow-up examinations;

In addition, due to the use of Atropine in subjects who have not reached targeted heart rate with peak dobutamine infusion, subjects with the following will be excluded:

- Glaucoma;
- Pyloric stenosis;
- Prostatic hypertrophy.

5.4.3 Discontinuation Criteria

Clearly document the reason for the subject's discontinuation on the Case Report Form (CRF). Discontinued subjects are not replaced. Discontinue a subject from the study if the subject:

- Withdraws consent;
- No longer meets the Inclusion Criteria;
- Experiences any of the Exclusion Criteria;
- Has an adverse event that, in the opinion of the Investigator, requires the subject's discontinuation. Perform subject follow-up in accordance with Section 9.1.5.

6 Investigational Product/Investigational Medicinal Product

The investigational product (IP)/investigational medicinal product (IMP) is LUMASON/SONOVUE.

In the USA and Canada, LUMASON will be supplied as a single 3-part kit with the following components:

- 1 clear glass vial labeled as LUMASON (sulfur hexafluoride lipid-type A microspheres) for injectable suspension,

- 1 prefilled syringe containing 5 mL Sodium Chloride 0.9% Injection, USP (Diluent) and its plunger rod
- 1 Mini-spike

In Europe, SONOVUE will be supplied in a kit which includes 2 individual plastic containers each with the following components:

- 1 vial containing 25 mg of lyophilized powder labeled as SONOVUE
- 1 pre-filled syringe containing 5 mL sodium chloride NaCl 0.9%w/v and its plunger rod
- 1 MiniSpike transfer system

6.1 Description and Labeling

LUMASON is formulated as a 25-mg sterile, non-pyrogenic lyophilized powder in a septum-sealed vial. The ingredients in each vial of LUMASON, after reconstitution, are listed in Table A

Table A: Description of Investigational Product/Investigational Medicinal Product

Ingredient	Concentration / Amount per Unit
Polyethylene glycol (PEG) 4000	4.91 mg/ml
Phospholipids (DSPC/DPPG 1:1 w/w)	0.075 mg/ml
Palmitic Acid	0.008 mg/ml
Sulfur Hexafluoride (SF6)	8 µL/ml*

*Contents in the microspheres/microbubbles

Each vial of LUMASON will bear a two-part label with the information detailed in Appendix A. Affix the second part of the two-part label from the vial to the vial label page.

6.2 Storage

Store the LUMASON kits at controlled room temperature at 25°C (77°F) excursions are permitted to 15-30 °C (59-86°F). No special storage conditions are required for SONOVUE containers. Do not freeze. All kits/containers must be stored in a secure area with limited access.

6.3 Blinding and Randomization

This is an open-label, nonrandomized study.

6.4 Handling and Preparation

Prior to administration, the lyophilized powder should be reconstituted under aseptic technique conditions by injecting the prefilled 5 mL sodium chloride syringe into the LUMASON/SONOVUE vial. After adding the sodium chloride solution, the vial should be shaken vigorously for 20 seconds, after which a homogeneous white milky liquid is obtained.

Detailed instructions for the reconstitution of both LUMASON and SONOVUE are presented in Appendix B.

Store the reconstituted IP/IMP at room temperature in the vial supplied. Although the suspension is useable for up to 3 hours in the USA and up to 6 hours in Canada/ Europe the more conservative time period of 3 hours will be used in this study. Upon standing for more than 15 minutes, buoyancy causes some of the larger microspheres/microbubbles to rise to the surface. Therefore, gently agitate the reconstituted vial in a top-to-bottom manner to resuspend the sulfur hexafluoride microspheres/microbubbles before administration.

A separate kit/container should be used for the rest (CEUS) and stress (CE-DSE) LUMASON administrations. In the case of incomplete use of vial contents, the product cannot be reused.

6.5 Administration

Once reconstituted, LUMASON will be administered as a single 2 mL bolus injection during the rest examination, and then again as a single 2 mL bolus injection after peak stress is achieved with the administration of the stress agent, dobutamine (with or without the addition of atropine), and the UE-DSE stress examination is completed. Each LUMASON injection will be performed intravenously through a peripheral line using a 20 gauge catheter followed immediately with 5 mL of saline in order to flush the intravenous line of any remaining contrast agent. There will be at least a 30 minute period between the rest and the stress LUMASON injections.

6.6 Accountability

In accordance with International Conference of Harmonization (ICH) and United States (US) FDA requirements, the Investigator and/or Drug Dispenser must at all times be able to account for all IP/IMP furnished to the institution. The appropriate site personnel must sign, date and immediately forward to the Sponsor the IP/IMP receipt form included with each shipment.

No IP/IMP is to be used outside of this study. Record the use of the IP/IMP on the appropriate Drug Accountability Record. All containers of IP/IMP must be accounted for, whether used or unused, during the course of and at the conclusion of the study. At the conclusion of the study, all shipments of IP/IMP to the Investigator must be returned to the Sponsor accompanied by a completed, signed copy of the appropriate IP/IMP inventory reconciliation form.

7 Non-Investigational Medicinal Products

7.1 Dobutamine

Dobutamine is a non-investigational medicinal product (NIMP) in this study due to its use as the pharmacologic stress agent during stress echocardiographic imaging. Refer to the dobutamine Package Insert (PI)/Summary of Product Characteristics (SPC) for details on the storage, handling, preparation and administration.

7.2 Atropine

Atropine is a non-investigational medicinal product (NIMP) in this study due to its use as an adjunct to dobutamine in achieving peak stress during DSE. Refer to the atropine PI/SPC for details on the storage, handling, preparation and administration.

8 Methodology

8.1 Study Schedule

See Appendix C for the timing of required observations and evaluations.

8.2 Written Informed Consent

Obtain written Informed Consent from the subject prior to the implementation of study procedures required by the protocol. The subject must sign the Informed Consent approved by the Institutional Review Board (IRB)/Ethics Committee (EC)/Research Ethics Board (REB) (including specific local requirements e.g., data protection where applicable). Give the subject a copy of the signed and dated written informed consent form including any other written information regarding the study. Document the Informed Consent process in detail in the source record at the site.

8.3 Subject Numbering

Assign a four digit subject number for each subject who qualifies for the study and signs the written Informed Consent. The first two digits of the subject number will be the investigational site number assigned by Sponsor. For site numbers less than ten use a leading zero. The third and fourth digits will be a number starting with 01 for the first subject enrolled and incrementing by "1" for each sequential subject.

For example, at site 01, the investigative site will assign the first subject 0101; the second subject 0102, etc.

Never reassign subject numbers. In the event that a subject withdraws from the study, the number assigned to that subject is retired and the next subject receives the next sequential number.

8.4 Subject Evaluations

8.4.1 Demographics

Obtain demographic information on each subject (including; height, weight, age, sex and race) and record on the CRF.

8.4.2 Medical History

Obtain a general medical history with relevant findings along with a special focus on cardiac history after the subject has signed the Informed Consent and within 24 hours prior to the first LUMASON administration. Record the subject's medical history/cardiac history on the appropriate Medical History or Cardiac Medical History sections of the CRF.

8.4.3 Pregnancy Test

If the subject is female, and of child bearing potential, exclude the possibility of pregnancy:

- by testing (serum or urine β HCG) within 24 hours prior to the start of IP/IMP administration;
- by surgical history (e.g., tubal ligation or hysterectomy);
- post-menopausal with a minimum of 1 year without menses.

8.4.4 Concomitant Medications

Record all medications (prescription and over-the-counter) taken within 24 hours prior to the first LUMASON administration in the Concomitant Medication section of the CRF. Additionally, record newly prescribed pharmacological treatments in this section up through 24 hours after the last LUMASON administration. Any medication taken for treatment of an adverse event that occurred after the subject signed the informed consent form should be recorded.

Record administration time and dosage information for medications administered as part of the pharmacologic stress procedure in a separate section on the CRF. Do not record on the concomitant medication CRF page.

8.4.5 Safety Assessments

8.4.5.1 Adverse Events

Monitor subjects for any untoward medical occurrences from the time of signing of Informed Consent through 72 hours after the last LUMASON administration or until the subject undergoes cardiac intervention, whichever comes first. Adverse events will be collected at the 24 hour postdose visit with a follow up phone call/contact at 72 hours. Any untoward medical occurrences as a result of the administration of the NIMP(s) (dobutamine or atropine) will also be considered adverse events. However, the known response pattern resulting from the administration of NIMP(s) for the purpose used in this study will not be recorded as adverse events.

Record all untoward medical events in the Adverse Event section of the CRF as specified in Section 9. Only postdose untoward medical occurrences will be tabulated as adverse events.

All serious adverse events that occur during the study monitoring period are required to be collected regardless of the relationship to LUMASON or the NIMPs on the Serious Adverse Event Report (SAER) Form.

In addition, the investigator should report any serious adverse events that occur after the monitoring period that he/she believes may be related to the LUMASON or the NIMPs on the SAER Form.

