10.5 Safety Analysis

The safety data will be summarized for all subjects dosed. Summary tables, including clinically significant changes wherever applicable, will be presented for the following safety endpoints:

- Adverse Events
- Clinical Laboratory Evaluations
- Electrocardiograms
- Vital Signs
- Special Situations

For vital signs and ECGs, the baseline for time points at rest will be the last measurement prior to the IP/IMP administration at rest; while the baseline for time points at stress will be the measurement which is collected after administration of the pharmacologic stress agent, dobutamine, and prior to LUMASON administration at stress (CE-DSE). All adverse events will be coded by MedDRA and summarized by system organ class and preferred term, by intensity and by causal relationship to the IP/IMP. Adverse event will be summarized separately for the NIMP(s). Only those events which occur from the start of IP/IMP administration through the follow-up period defined in the protocol will be tabulated in the Clinical Trial Report as “adverse events” see Section 9.1.1.

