Appendix C: Study Schedule

Event	Rest						Stress					Follow-Up		
	UEUS				IP/IMP	CEUS	STRESSOR	UE-DSE	IP/IMP	CE-DSE		24 hr	72 hr	6 mos
	Within -24 hr	-1 hr	-10 min	Immed prior	0 min	30 min		Immed prior	0 min	30 min	1 hr			
Written Informed Consent ^a	x													
Pregnancy Test (if necessary)	x													
Adverse Events Monitoring ^b	x	⇒	⇒	⇒	⇒	⇒	⇒	⇒	⇒	⇒	⇒	⇒	x	
Concomitant Medications ^c	x	⇒	⇒	⇒	⇒	⇒	⇒	⇒	⇒	⇒	⇒	x		
Medical History ^d	x													
Physical Examination	x											x		
Vital Signs ^{e,f}		x				x		x		x	x	x		
Laboratory Evaluations ^g	x											x		
Electrocardiogram - discrete ^f		x				x		x		x	x	x		
Electrocardiogram – continuous			x	⇒	⇒	⇒	⇒	⇒	⇒	x				
Pulse oximetry			x	⇒	⇒	⇒	⇒	⇒	⇒	x				
IP/IMP Administration					x				x					
Imaging Procedure				x	x			x	x					
Dobutamine Administration ^h							x							
Truth Standard												x	⇒	x
Follow-up Contact for AE													x	

^a Obtain prior to implementation of any study procedure.

^b Start monitoring from the time of signing Informed Consent up to 72 h after the last LUMASON administration or until cardiac intervention, whichever comes first. Collect adverse events for LUMASON and NIMPs (dobutamine, atropine).

^c Record all medications (prescription and over-the-counter) taken within 24 hours prior to first LUMASON administration up through 24 hours after the last LUMASON administration.

^d Includes Demographics, Cardiac Medical History and General Medical History.

[figure not shown]
^e Includes systolic and diastolic blood pressure, heart rate.

[figure not shown]
^f If stress echocardiography (CE-DSE) is not performed, obtain at 1 and 24 hours after the rest LUMASON administration.

[figure not shown]
^g Collect blood samples according to the instruction manual from the central laboratory.

[figure not shown]
^h Atropine may be administered with dobutamine if needed to achieve peak stress.

[figure not shown]

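### Adverse-event collection and tabulation stop at an undefined cardiac intervention if it comes before 72 hours, so new events after it can be lost for a reason linked to how the subject fared after dosing

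*Combined protocol and SAP*

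**What the plan says.** Three places set the window, and they agree. Section 8.4.5.1 runs monitoring from consent to "72 hours after the last LUMASON administration or until the subject undergoes cardiac intervention, whichever comes first". Section 5.3 says that safety monitoring as a whole will "continue for 72 hours after the last LUMASON administration or until the subject undergoes cardiac intervention, whichever comes first". Footnote b of Appendix C has "up to 72 h after the last LUMASON administration or until cardiac intervention, whichever comes first". None of them defines cardiac intervention or separates urgent from elective procedures.

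The window governs three other rules:

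- **Serious events inside it.** Section 8.4.5.1: "All serious adverse events that occur during the study monitoring period are required to be collected regardless of the relationship to LUMASON" or the non-investigational products.
- **Serious events after it.** The investigator should still report "any serious adverse events that occur after the monitoring period that he/she believes may be related to the LUMASON or the NIMPs". Section 9 repeats this. Section 9.1.2 adds that such reports are not made on the Case Report Form.
- **Tabulation.** Section 10.5: "Only those events which occur from the start of IP/IMP administration through the follow-up period defined in the protocol will be tabulated" as adverse events. Section 9.1.1 does not require events after the period to be entered in the adverse-event section of the form.

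The contact schedule has no matching exception. Section 8.4.5.1: "Adverse events will be collected at the 24 hour postdose visit with a follow up phone call/contact at 72 hours". The 24-hour physical examination, vital signs, laboratory tests and ECG (Sections 8.4.5.2 to 8.4.5.5) are also written without one.

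**The concern.** A safety window should close at a time fixed in advance, or for a reason unrelated to what happened after dosing. Here it can close because of what happened after dosing: a subject who becomes ischemic after the stress dose may have an intervention for that reason. New events after that point then drop out of the adverse-event tables. Section 10.5 summarizes safety for all subjects dosed, and the text supplied describes no allowance for unequal follow-up.

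Obtaining safety data in this setting is a stated secondary objective (Section 4). Up to the intervention, serious events are collected whatever their cause. After it, reporting depends on the investigator's view of causality, at a time when the procedure itself offers a competing explanation (it is listed as one in Section 9.1.4).

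The 6-month follow-up is not a reliable backstop. It is required only of subjects with no angiography or an indeterminate one (Section 8.6.4.2), and it collects cardiac events for the truth standard, not adverse events.

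**Working it through.** The plan gives no figure to reproduce. The check sets the rules side by side for a subject who has a cardiac intervention less than 72 hours after the last dose.

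| Event | Onset before the intervention | Onset after it, within 72 h |
|---|---|---|
| Non-serious adverse event | Collected and tabulated (8.4.5.1, 10.5) | Not required on the form (9.1.1), not tabulated (10.5) |
| Serious event not judged related | Collected and tabulated | No requirement to collect it, not tabulated |
| Serious event judged possibly related | Collected and tabulated | Reported to the sponsor (8.4.5.1, 9, 9.1.2), kept off the form (9.1.2), not tabulated as an adverse event (10.5) |

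An event that began before the intervention stays in the data. Section 9.1.5 has it followed until it settles or is judged irreversible, and Section 9.1.4 includes death among the outcomes to be recorded. The loss is therefore confined to the right-hand column.

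**Length of window lost.** For an intervention at t hours after the last dose, the share of the post-dose window lost is (72 − t)/72. The documents give no intervention times, so these values of t are assumptions for illustration:

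- t = 6: (72 − 6)/72 = 66/72 = 92%
- t = 24: (72 − 24)/72 = 48/72 = 67%
- t = 48: (72 − 48)/72 = 24/72 = 33%

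These are shares of one subject's window. They do not measure bias in the trial's event rates, which also depends on how many subjects have an intervention and how many new events follow. The documents give neither number.

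**Conflict with the assessments.** Take an assumed intervention at 10 hours. Under Section 5.3, safety monitoring has ended. Under Sections 8.4.5.2 to 8.4.5.5, the 24-hour examination, vital signs, blood sample (which includes troponin) and ECG are still due. Sections 8.4.5.2, 9.3.1, 9.4, 9.6 and 9.7 send qualifying changes found at those assessments to the adverse-event section of the form. Section 9.1.1 says an event after the follow-up period need not be entered there, and Section 10.5 would not tabulate it. A site cannot tell from the text whether a new abnormality at 24 hours is to be recorded as an adverse event. The 72-hour contact raises the same question.

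**The case against.** The best case for the plan has four parts.

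1. **Serious events do not simply stop.** A reader might infer that all serious-event reporting ends at the intervention. It does not: those the investigator believes may be related remain reportable, with no end date. The causality threshold is also low, because Section 9.1.4 puts events with conflicting or insufficient evidence in the reasonable-possibility class. This stands as far as reporting goes. It does not put the event in the tables, because such reports stay off the form and outside the tabulated period.
2. **The deterioration is captured.** A reader might infer that subjects who worsen and need urgent intervention vanish from the safety data. They do not: the index event precedes the cut-off, is collected whatever its cause, and is followed to outcome. If it was serious, the subject already counts as having a serious event, and a later one does not change the proportion of subjects affected. This stands in full and narrows the point to new-onset events.
3. **Few subjects may be affected.** Section 5.4.2 excludes unstable angina, acute coronary syndrome, left main stenosis and infarction within 30 days, and angiography may take place up to 6 months after the examination (Section 5.4.1). A reader might infer that diagnostic catheterization triggers the cut-off. The text does not say so, and elsewhere it uses coronary angiography when it means that. But with no definition, sites could differ.
4. **The cut-off has a purpose.** Stopping at the intervention plausibly keeps procedural complications from being read as effects of the agent. That is a fair aim, but the documents do not state it, and it can be met by labeling the events instead of dropping them.

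The absence of a safety board (Section 11.5) adds nothing here, since a board does not set the collection window.

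**Conclusion.** The point holds in a limited form. As written, new-onset non-serious events, and serious events not judged related, that occur after a cardiac intervention but within 72 hours are not required to be collected. Serious events judged related are reported to the sponsor but not tabulated as adverse events. Because an intervention can follow a post-dose deterioration, this truncation can be informative, and omitted events can only lower the tabulated counts. Separately, the cut-off is inconsistent with the 24-hour assessments and the 72-hour contact, and must be reconciled with them whatever view is taken of the cut-off itself.

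The size is unknown. The documents state neither the number of interventions expected within 72 hours nor their timing, so a reader who infers a definite downward bias in the serious-event rate goes further than they allow. Nor is the cut-off confined to the sickest subjects: any cardiac intervention, elective ones included, would trigger it. The conclusion rests on reading the follow-up period in Sections 9.1.1, 9.1.2 and 10.5 as the one defined in Section 8.4.5.1, which Section 9 says it is. It is a worthwhile, inexpensive improvement to the safety data and leaves the efficacy analysis untouched.

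**What to change.** - In Section 5.3, Section 8.4.5.1 and Appendix C footnote b, remove the intervention cut-off for data collection, so that events are collected through 72 hours after the last dose in every dosed subject. At minimum do this for all serious events and deaths, regardless of relationship.
- Align Section 9.1.2, so that serious events within 72 hours go on the form, and Section 10.5, so that they are tabulated.
- Record the date, time and type of any cardiac procedure in the window, and present events before and after it separately. If any cut-off is kept for non-serious events, define cardiac intervention and say whether diagnostic catheterization counts.
- State that the 24-hour assessments and 72-hour contact apply whether or not there has been an intervention.

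The cost is protocol wording, a short procedure entry on the Case Report Form and one split in the adverse-event tables. The 72-hour contact is already planned. The downside is that a few procedure-related events will be collected, which the before-and-after presentation handles. Only data collection and tabulation change, not clinical management.
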